3. INTRODUCTION

3.1. Study Rationale

This open-label study in 6 healthy male participants will assess the excretion balance of GSK2269557 in humans, using [¹⁴C]-radiolabelled drug substance administered orally and as an intravenous (IV) infusion. [¹⁴C]-GSK2269557 administered by IV infusion will be a microtracer; therefore, it will be administered concomitantly to an inhaled non-radiolabelled dose. This will be done in order to ensure that the pharmacokinetics represent a clinically relevant dose. The study will also provide an assessment of the bioavailability of GSK2269557 following oral and inhaled administration.

The pharmacokinetics, absorption, distribution and metabolism of GSK2269557 have been investigated through a series of IV, oral, intratracheal or inhaled studies in animals, and in *in vitro* studies using unlabelled GSK2269557. Only preliminary data are available so far for in human pharmacokinetics. GSK2269557 has been administered to humans in several clinical trials all via the inhalation route across a range of doses up to 3200 mcg twice daily for 7 Days in healthy volunteers and up to 1000 mcg once daily for 84 Days to exacerbating chronic obstructive pulmonary disease (COPD) patients. Definitive absorption, distribution, metabolism and excretion (ADME) characteristics derived from this study will provide important understanding of GSK2269557 in human including routes of elimination and metabolic pathways.

This study will use the Entero-Test (Entero-Test: HDC Corp., Mountain View, CA; or alternative source subject to commercial availability) for sampling of duodenal bile to conduct qualitative assessment of drug metabolites in this matrix in order to characterise biliary elimination pathways.

Samples from this study will also be used to characterise, where possible, and quantify the metabolites of GSK2269557 in plasma, urine, faeces and duodenal bile.

3.2. Background

GSK2269557 is a potent and highly selective inhaled phosphoinositide 3-kinase (PI3K)-delta (δ) inhibitor, being developed as an anti-inflammatory agent for the treatment of COPD and other inflammatory lung disease such as asthma. PI3K δ is a member of the Class IA family of PI3Ks, that converts the membrane phospholipid phosphatidylinositol 4,5-biphosphate (PIP2) into phosphatidylinositol 3,4,5-trisphosphate (PIP3). PIP3 is a second messenger in many cellular processes including cell growth, differentiation and migration.

PI3K δ has specific roles in mediating antigen receptor and cytokine signalling in T-cells, mast cells and B-cells PI3K δ is thought to play an important part in various epithelial responses relevant for the development of COPD and asthma.

COPD is an umbrella term for the two disease processes: chronic bronchitis and emphysema. COPD invariably has a degree of both, though one phenotype/process may predominate in any individual. Inflammation has been linked to the pathogenesis of COPD. Tobacco smoke or other irritants activate epithelial cells and macrophages to

release inflammatory mediators, such as chemokines, that attract neutrophils and T-cells to the lungs. Both neutrophil and T-cell are targets of PI3K δ inhibitors.

Chronic inflammation in the lung is also linked to the pathogenesis of asthma. Inflammation in asthma is associated with a T-cell response to allergens in the lung, with Th2 cytokines driving the differentiation, survival and function of the major effector cells involved in the allergic cascade. Th2 cells also play an essential role in the increased production of allergen-specific Immunoglobulin E (IgE) by B-cells. IgE mediates type I hypersensitivity allergic responses and the orchestration of local chronic allergic inflammation. Therefore, suppression of the Th2 drive in the lung has the potential to be disease modifying in asthma patients. GSK2269557 has been shown *in vivo* to potentially block T-cell activation in the lung, via reducing the production of pro-inflammatory Th2 cytokines interleukin (IL)-13, IL4 and IL-5, thus preventing recruitment of inflammatory cells to the lung.

As a PI3K δ inhibitor, GSK2269557 has the potential to inhibit the major cell types responsible for the inflammation associated with both COPD and asthma. GSK2269557 has already been administered as a nebulised solution and dry powder formulation in single and repeated doses to humans and has been well tolerated across the range of doses used. A detailed description of the chemistry, pharmacology, efficacy, and safety of GSK2269557 is provided in the Investigator's Brochure [GlaxoSmithKline Document Number [2012N141231_07](#)].

3.3. Benefit/Risk Assessment

More detailed information about the known and expected benefits and risks and reasonably expected adverse events of GSK2269557 may be found in the Investigator's Brochure[GlaxoSmithKline Document Number [2012N141231_07](#)]. Section 3.3.1 outlines the risk assessment and mitigation strategy for this protocol:

3.3.1. Risk Assessment

Potential Risk of Clinical Significance	Summary of Data/Rationale for Risk	Mitigation Strategy
Investigational Product [e.g. GSK2269557]		
Radioactivity exposure risk (¹⁴C)-GSK2269557)	
The total effective dose associated with IV and oral administrations of [¹⁴C]-GSK2269557 is 0.75 mSv. That effective dose is within the lower end of WHO recommendation (0.5 to 5 mSv) for Category II projects, which is considered to be within dose limits for members of the public. The total effective dose is also below the GlaxoSmithKline Global Safety Board level of radiation which would require specific additional justification and exemption (10 mSv).
	
Participants will be monitored for recovery of radioactivity throughout the study.

Bronchospasm	
Can potentially occur with any inhaled treatment.
	
All doses of study treatment will be administered in the clinical pharmacology unit in the presence of trained clinical staff.
 
Treatment with a short-acting inhaled bronchodilator will be available. GSK2269557 should be discontinued immediately, the participant assessed and, if necessary, an alternative therapy instituted as deemed appropriate by the investigator or the attending physician. Participants will be withdrawn from the study.

Potential Risk of Clinical Significance	Summary of Data/Rationale for Risk	Mitigation Strategy
Mucosal irritancy	Detected in 13 week toxicology study in the dog.	Participants will be regularly monitored for AEs. No evidence of mucosal irritancy has been seen so far in clinical studies.
Exposure to GSK2269557	The total systemic exposure of GSK2269557 from the combined IV microtracer (10 µg) and inhaled dose (1000 µg) is predicted to be below the systemic exposure from the highest dose of GSK2269557 tested in previous human studies (a single inhaled nebulised dose of 6400 µg). The oral dose to be tested is 800 µg. Overall GSK2269557 has been well tolerated in previous clinical studies and has an acceptable safety profile. The most commonly observed AEs have been cough and headache.	In addition to taking samples for pharmacokinetic analysis of GSK2269557, pharmacodynamic markers of GSK2269557 will be monitored: HR and QTc measurements will be taken, haematology and clinical chemistry will be monitored as part of the panel of laboratory safety tests.

Potential Risk of Clinical Significance	Summary of Data/Rationale for Risk	Mitigation Strategy
Study Procedures		
Intravenous Dosing – Pain at the injection site	
GSK2269557 has not previously been administered by IV infusion in humans. Doses of 12 µg/kg, 360 µg/kg and 1200 µg/kg of GSK2269557, dissolved in a 5% dextrose in water solution, were given as a 1 hour IV infusion (5 mL/kg/hr dosing volume) to male rats, in a rat cardiovascular study. No irritancy at site of injection has been reported for the study.
	
 Participants will be monitored for signs of pain at the injection site. Paracetamol or Acetaminophen, at doses of ≤ 2 g/day can be taken if required.
Entero-Test for bile collection risk	
The use of the Entero-Test has been approved by the European regulatory authorities (ISO 9001 and CE Mark Certification; European Union Medical Devices Directive (MDD)).
 
 Streaks of blood on the string due to local irritation have been infrequently noted. Rarely, a patient will be unable to swallow the capsule because of gagging or will vomit after doing so. Gagging upon retrieval of the string can occur. On a few occasions, an entire string has been swallowed without ill effects and passes out from the body in the faeces. 	
 The string will be securely taped in place (to the cheek of each individual) during the collection time to minimise risk of swallowing the entire string. Any participant incapable of swallowing the string will be allowed to participate in the study without duodenal bile collection.

Potential Risk of Clinical Significance	Summary of Data/Rationale for Risk	Mitigation Strategy
Study Population		
Post-inhalation cough immediately following inhalation of study treatment (GSK2269557)	Treatment-related, mild and moderate cough (preferred term) were reported as adverse events (AEs), immediately after dosing, in previous studies of GSK2269557 conducted in both healthy participants and exacerbating COPD patients. Additional details are provided in the Investigator's Brochure [GlaxoSmithKline Document Number 2012N141231_07].	In this study, healthy participants will receive a single inhaled dose during treatment period 1. Participants will be in the presence of clinical staff during their 7-day post-dose residence at the clinical pharmacology unit and will be regularly monitored for AEs.
Inclusion of volunteers >30 years and <55 years (inclusive)	Justification of the use of healthy volunteers below the age of 50 years is required in accordance with the guidelines of the Administration of Radioactive Substances Advisory Committee and the Association of the British Pharmaceutical Industry, as well as GSK internal policies. In this study, healthy male volunteers between 30 and 55 years will be enrolled. This is acceptable, because the total effective dose of this study is considered to be within variations in natural background radiation with a minimal risk.	Not applicable.

3.3.2. Benefit Assessment

Healthy participants in this study will receive no direct medical benefit. However, they may benefit from the knowledge that they are contributing to the process of developing a new treatment in an area of unmet need. They might also benefit from the thorough medical assessments they receive during the course of the study.

3.3.3. Overall Benefit:Risk Conclusion

It is considered acceptable to conduct this study in healthy participants, because whilst they will receive no direct medical benefit, the risks from the study treatment and procedures are minimal. The study will be conducted in a fully equipped clinical pharmacology unit with access to hospital emergency facilities.

4. OBJECTIVES AND ENDPOINTS

Objectives	Endpoints
Primary	

 To determine total radioactivity (drug related material) in plasma following a single IV microtracer of [¹⁴C]-GSK2269557 (concomitant with an inhaled non-radiolabelled GSK2269557 dose) and a single oral dose of [¹⁴C]-GSK2269557. 	
 AUC(0-inf), AUC(0-t), Cmax, tmax, t_{1/2} of total drug-related material (radioactivity) in plasma.

 To determine the rate and extent of excretion of total radioactivity in urine and faeces and the total recovery of radioactivity following a single IV microtracer of [¹⁴C]-GSK2269557 (concomitant with an inhaled non-radiolabelled dose) and a single oral dose of [¹⁴C]-GSK2269557. 	
 Urinary and faecal cumulative excretion as a percentage of the total radioactive dose administered over time.
Secondary	

 To determine parent GSK2269557 concentration in plasma following a single IV microtracer of [¹⁴C]-GSK2269557 (concomitant with an inhaled non-radiolabelled GSK2269557 dose) and a single oral dose of [¹⁴C]-GSK2269557. 	
 AUC(0-inf), AUC(0-t), Cmax, tmax, and t_{1/2} of parent GSK2269557 and [¹⁴C]-GSK2269557¹ in plasma. Volume and clearance of parent [¹⁴C]-GSK2269557¹ after IV dose only.

 To estimate the absolute bioavailability of GSK2269557 following inhaled and oral administration. 	
 Oral and inhaled F (absolute bioavailability).

Objectives	Endpoints

 To evaluate the safety and tolerability of GSK2269557 after single IV, oral and inhaled doses in healthy participants. 	
 Incidence of adverse events Laboratory safety, electrocardiogram (ECG) and vital signs parameters.
Exploratory	

 To generate samples that will be used to characterise the metabolic profile of GSK2269557 in plasma, urine, faeces, and duodenal bile (following IV dose only), following a single IV microtracer of [¹⁴C]-GSK2269557 (concomitant with an inhaled non-radiolabelled dose) and a single oral dose of [¹⁴C]-GSK2269557 (these analytical investigations will be conducted and the results reported under a separate Platform Technology Services (PTS) In vitro/In vivo Translation (IVIVT), GlaxoSmithKline protocol). 	
 Characterisation and quantification of metabolites in plasma, urine, faeces, and duodenal bile (these analytical investigations will be conducted and the results reported in a separate GSK PTS IVIVT protocol).

[figure not shown]
¹ For measured concentrations of GSK2269557 in blood plasma, the nomenclature [¹⁴C]-GSK2269557 describes the parent GSK2269557 concentration derived via analysis by LC+AMS, whereas GSK2269557 describes the parent GSK2269557 concentration derived via LC/MS.

5. STUDY DESIGN

5.1. Overall Design

This is an open-label, single centre, non-randomised, 2-period, single-sequence crossover, mass balance study to investigate the recovery, excretion, and pharmacokinetics of [¹⁴C]-GSK2269557 administered as a single IV dose (concomitant with an inhaled non-radiolabelled dose) and a single oral dose, in healthy male participants.

Each participant will participate in the study for up to 11 weeks, and will have a screening visit, 2 treatment periods, and a follow up visit (see [Figure 1](#)). If excretion is higher than 1%, or if the results are inconclusive, upon discharge on Day 15 (if participants haven't been discharged before then), participants will continue to collect faecal samples only, at home, at 24-h intervals which will be returned to the clinic every 2-3 days.

Figure 1 Study design schematic.

*If radioactivity excretion is higher than 1% upon discharge, faecal samples will be collected by participants at home after Day 15 (day of discharge/follow-up).

5.1.1. Screening Period

Participants must be screened within 30 days before the first dose, and must meet all eligibility criteria.

5.1.2. Study Periods

The study will be divided into treatment periods 1 (concomitant IV and inhaled dosing) and 2 (oral dosing). In each treatment period, participants will be resident in the unit from the afternoon before Day 1 (Day -1).

On Day 1 of treatment period 1, after an overnight fast of at least 8 h, each participant will take 1000 µg non-radiolabelled GSK2269557 by inhalation. Within 5 min after the inhalation, participants will receive 10 µg [¹⁴C]-GSK2269557 (approximately 22.2 kBq; 0.6 µCi) by IV infusion over 15 min. Following dosing, blood, duodenal bile, urine and faecal samples will be collected up to 168 h after dosing (Day 8).

Participants will be discharged on Day 8 after completion of the 168-h post-IV dosing sample collection. There will be a washout of at least 14 days after inhaled and IV dosing before participants take the oral dose of GSK2269557 in treatment period 2.

On Day 1 of treatment period 2, after an overnight fast of at least 8 h, each participant will take 800 µg [¹⁴C]-GSK2269557 (50 µCi or 1850 kBq) as an oral solution. Following dosing, blood, urine and faecal samples will be collected for a minimum of 168 h (up to Day 8), but could be up to 336 h (Day 15) or longer after dosing, depending on the amount of radioactivity excreted by each participant. Liquid scintillation counting (LSC) will be performed daily on 24 h urine collections and 24 h faecal homogenates after Day 6 (at 144 h and 168 h from dosing).

- If less than 1% of the dose is excreted in each 24-h period on Day 6 (120–144 h) and Day 7 (144–168 h) for a given participant, that participant may be discharged as early as Day 8 (after the LSC results are available), and no further samples will be collected.
- If excretion is higher than 1%, or if the results are inconclusive in each 24-h period on Day 6 (120-144h) and Day 7 (144-168h) for a given participant, the participant will remain at the unit, and urine and faecal collections will continue at 24-h intervals, for up to 7 days (until the morning of Day 15). If less than 1% of the dose is excreted in any of the 24-h periods between Day 7 and Day 15, that participant will be discharged. All remaining participants will be discharged from the unit on Day 15.
- In the unlikely event that excretion is still higher than 1% upon discharge on Day 15, the participants will continue to collect faecal samples only, at home, at 24-h intervals. Samples will be returned to the unit every 2–3 days for analysis.

The Entero-Test to measure duodenal bile will be used (subject to commercial availability) only for Treatment 1 (IV dosing). The Entero-Test will be inserted about 3.5 h before the start of the IV infusion while participants are in a fasted state, and it will be removed about 2.5 h after the end of the IV infusion. About 0.5 h after the end of the IV infusion (2 h before string withdrawal) a food cue will be used to stimulate gall bladder emptying.

Plasma samples will be prepared (from collected blood samples) to measure parent drug (GSK2269557, [¹⁴C]-GSK2269557) and total radiolabelled drug-related material. Urine and faecal samples will be collected to measure total radiolabelled drug-related material. Samples of plasma, urine, bile and faeces will also be transferred to a separate study to characterise and, where possible, quantify metabolites in those matrices.

Safety data will include AE reporting, 12-lead ECG, vital signs, and laboratory safety tests.

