Number of Participants: 6 healthy male participants.

Treatment Groups and Duration: Each participant will participate in the study for up to 11 weeks, and will have a screening visit, 2 treatment periods, and a follow-up visit. In each treatment period, participants will be resident in the unit from the morning before Day 1 (Day -1).

On Day 1 of treatment period 1, after an overnight fast of at least 8 h, each participant will take 1000 µg non-radiolabelled GSK2269557 by inhalation. Within 5 min after the inhalation, participants will receive 10 µg [¹⁴C]-GSK2269557 (approximately 22.2 kBq; 0.6 µCi) by IV infusion over 15 min. Following dosing, blood, duodenal bile, urine and faecal samples will be collected up to 168 h after dosing (Day 8). Participants will be discharged on Day 8 after completion of the 168-h post-IV dosing sample collection. There will be a washout of at least 14 days after inhaled and IV dosing before participants take the oral dose of [¹⁴C]-GSK2269557 in treatment period 2.

On Day 1 of treatment period 2, after an overnight fast of at least 8 h, each participant will take 800 µg [¹⁴C] -GSK2269557 (approximately 1850 kBq; 50 µCi) as an oral solution. Following dosing, blood, urine and faecal samples will be collected for a minimum of 168 h (up to Day 8), but could be up to 336 h (Day 15) or longer after dosing, depending on the amount of radioactivity excreted by each participant. Liquid scintillation counting (LSC) will be performed daily on 24-h urine collections and 24-h faecal homogenates after Day 6 (at 144 h and 168 h from dosing).

- If less than 1% of the dose is excreted in each 24-h period on Day 6 (120-144 h) and Day 7 (144-168 h) for a given participant, that participant may be discharged as early as Day 8 (after the LSC results are available), and no further samples will be collected.
- If excretion is higher than 1%, or if the results are inconclusive, in each 24-h period on Day 6 (120-144 h) and Day 7 (144-168 h) for a given participant, the participant will remain at the unit, and urine and faecal collections will continue at 24-h intervals, for up to 7 days (until the morning of Day 15). If less than 1% of the dose is excreted in any of the 24-h periods between Day 7 and Day 15, that participant will be discharged. All remaining participants will be discharged from the unit on Day 15.

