Drugs of abuse	X										
Alcohol and cotinine tests ⁴	X										
Brief Physical Exam		X								X	
Laboratory safety tests	X	X		X					X	X	
12-lead ECG	X	X	X ⁵	X					X	X	
Vital signs (HR and BP)	X	X	X ⁵	X					X	X	
Oral dose			X								
Blood samples for total radioactivity, [¹⁴ C]-GSK2269557 analysis and cold GSK2269557 analysis		X ⁶	X	X	X	X	X		X		
Blood samples for metabolite profiling		X	X ⁷	X							
Urine collection ^{8,9}		X	X	X	X	X	X	X	X		
Faecal collection ^{10,11}		X ¹¹	X	X	X	X	X	X	X	X ¹²	
Meals ¹³			X								

Procedure	Treatment Period 2 (Oral dosing)									Follow-up (7-14 days post-last dose) ^{2,3}	
	Day										
	-1	1 ¹	2	3	4	5	6	7	8		
AE/concomitant medication review ¹⁴		←	→								

1. There will be a washout of at least 14 days between dosing in treatment period 1 and 2.
2. If less than 1% of the dose is excreted in each 24 h period on Day 6 (120-144 h) and Day 7 (144-168 h) for a given participant, the participant may be discharged as early as Day 8 (after the LSC results are available), and no further samples (apart from for laboratory safety tests) will be collected. Follow-up procedures may be done at discharge and procedures scheduled for Day 8 and follow up will only be done once.
3. If excretion is higher than 1%, or if the results are inconclusive in each 24-h period on Day 6 (120-144 h) and Day 7 (144-168 h) for a given participant, that participant will remain at the unit, and urine and faecal collections will continue at 24-h intervals, for up to 7 days (until the morning of Day 15), until excretion is less than 1%. All remaining participants will be discharged from the unit on Day 15. Follow-up procedures may be done at discharge. In the unlikely event that excretion is still higher than 1% upon discharge on Day 15, participants will continue to collect faecal samples only, at home, at 24-h intervals. Samples collected at home will be returned to the clinic every 2-3 days.
4. Breath test will be performed to check alcohol consumption. Both CO breath tests and urine cotinine tests will be performed to check smoking state.
5. Vital signs and ECG will be taken 6 h post dose.
6. Sampling times relative to the oral dose. Blood samples for total radioactivity, [¹⁴C]-GSK2269557 analysis and cold GSK2269557 analysis will be taken: pre-dose and at 0.25, 0.5, 0.75, 1, 2, 3, 4, 6, 8, 10, 12, 16, 24, 48, 72, 96 and 168 h post-dose.

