7. Blood samples for plasma metabolite profiling will be collected at 2 h and 6 h post-[¹⁴C]-GSK2269557 oral dose.
8. An aliquot from each urine collection will be taken for metabolic profiling (separate study).
9. Urine will be collected at pre-dose, at 0-6 h, 6-24 h then over 24 h collection periods as follows: 24-48 h, 48-72 h, 72-96 h, 96-120 h, 120-144 h, 144-168 h.
10. An aliquot from each faecal collection will be taken for metabolic profiling (separate study).
11. The pre-dose faecal sample can be collected up to 24 h pre-dose. Afterward faeces will be collected over 24 h collection periods as follows: 0-24 h, 24-48 h, 48-72 h, 72-96 h, 96-120 h, 120-144 h, 144-168 h.
12. If dose excretion is still higher than 1% after day 15 the participants will continue to collect faecal samples only, at home, at 24-h intervals until excretion is less than 1%.
13. Meal times are 4h and 10h post dose on Day 1. On all other days, meals will be served at the standard times for the unit.
14. AEs and SAEs will be collected from the signing of the ICF until the follow-up visit. However, any SAEs related to study participation or a GSK concomitant medication will be recorded from the time a participant consents to participate in the study and until the final follow-up visit contact.

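### Period 2 (oral) only: read literally, one later 24-h period with no stool and little urinary radioactivity meets the below-1% rule and can cut short that participant's cumulative recovery, a primary endpoint; one sentence fixes it

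*Protocol*

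**What the plan says.** The rules below apply to the oral period only. Period 1 collection is fixed at 168 h.

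- **What is counted.** Protocol 5.1.2 has liquid scintillation counting done daily on "24 h urine collections and 24 h faecal homogenates after Day 6".
- **First check (Days 6 and 7).** Excretion must be below 1% of dose in each of 120-144 h and 144-168 h. The participant then *may* leave on Day 8, and no further samples are taken apart from safety bloods (5.1.2; SoA Period 2 footnote 2).
- **Who stays.** Participants stay if excretion is above 1%, "or if the results are inconclusive in each 24-h period on Day 6 (120-144h) and Day 7 (144-168h").
- **Later check.** The participant *will* be discharged if "less than 1% of the dose is excreted in any of the 24-h periods between Day 7 and Day 15" (5.1.2). The Synopsis has the same rule: "in any of the 24-h periods between Day 7 and Day 15, that participant will be discharged".
- **End of collection.** SoA footnote 3 continues urine and faecal collection "for up to 7 days (until the morning of Day 15), until excretion is less than 1"%.
- **After Day 15.** "If dose excretion is still higher than 1% after day 15 the participants will continue to collect faecal samples only", at home (SoA footnote 12). Section 5.1 alone extends this to inconclusive results: "or if the results are inconclusive, upon discharge on Day 15".

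Cumulative urinary and faecal excretion as a percentage of dose is a primary endpoint (Protocol 4).

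**The concern.** The first check needs two named periods and permits discharge. The later check needs any one period and requires discharge. It applies to participants whose excretion was above 1% or not clearly below it.

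With no stool there is no homogenate to count, so the measured output for that day is urine alone. Nothing in the protocol or SAP says that such a day does not qualify. *Inconclusive* is undefined. It is attached to Days 6/7 and, in 5.1, to Day 15, but not to the periods between. Home collection is planned only for participants still above 1% at Day 15, so it does not pick up someone released earlier.

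At stake is the completeness of oral recovery for that participant. Six are enrolled to obtain at least four completers (Protocol 10.1), so one truncated participant carries visible weight in the mean. Material that was never collected cannot be recovered by analysis. Plasma radioactivity and Period 1 are not affected.

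**Working it through.** **Inputs from the documents.** Oral dose 1850 kBq, so the 1% threshold is 0.01 × 1850 = 18.5 kBq. The extension runs from 168 h to 168 + 7 × 24 = 336 h (seven intervals). The plan gives no excretion rate, stool frequency or expected recovery beyond the entry criterion of an average of one or more bowel movements a day, so there is no plan figure to reproduce.

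**Assumptions.** Excretion in the Day 7 period r = 2, 3 or 5% of dose/day; half-life h = 2 or 4 days; chance p of a stool-free 24-h period 5% or 10%; retained material passes with the next stool; urine ignored unless stated; rule applied from 168-192 h. Everything is conditional on entering the extension, whose probability is unknown.

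**Step 1: what the rule sees.** If true output is 3% of dose and urine carries 10% of it (assumed), a stool-free day measures 3 × 0.10 = 0.30%, which is below 1%.

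**Step 2: hand check, slowest setting (r = 5, h = 4).** Output in extension interval i is 5 × 2^(−i/4): 4.20, 3.54, 2.97, 2.50, 2.10, 1.77, 1.49. With daily stools nobody stops early. A first stool-free day in interval i has probability p(1−p)^(i−1) and loses the sum of outputs from i onward: 18.57, 14.37, 10.83, 7.86, 5.36, 3.26 for i = 1 to 6.
- p = 0.05: 0.05 × (18.57 + 13.65 + 9.77 + 6.74 + 4.37 + 2.52) = 2.8
- p = 0.10: 0.10 × (18.57 + 12.93 + 8.77 + 5.73 + 3.52 + 1.93) = 5.1

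This is marginally high, because a stool-free last interval also lowers the total reachable by 336 h. It agrees with the simulated 2.8 and 5.1.

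**Step 3: all settings.** Simulation with 200,000 participants per setting. Loss = cumulative recovery to 336 h minus cumulative recovery at the stop, in % of dose. The part due to stool-free periods is the loss under the current rule minus the loss under a rule that needs a stool in the qualifying period.

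| r / h | Daily stools | Current rule, p = 5%, 10% | Due to stool-free periods, p = 5%, 10% |
|---|---|---|---|
| 2 / 2 | 1.3 | 1.5, 1.8 | 0.3, 0.7 |
| 2 / 4 | 1.3 | 2.0, 2.7 | 0.9, 1.7 |
| 3 / 2 | 1.2 | 1.7, 2.2 | 0.6, 1.2 |
| 3 / 4 | 0 | 1.7, 3.1 | 1.7, 3.1 |
| 5 / 2 | 1.1 | 2.2, 3.2 | 1.2, 2.3 |
| 5 / 4 | 0 | 2.8, 5.1 | 2.8, 5.1 |

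The daily-stool column is the output r × 2^(−i/h) left after the first interval below 1%. For 2/2 the outputs are 1.41, 1.00, 0.71, so collection stops at 216-240 h and 0.50 + 0.35 + 0.25 + 0.18 = 1.3 is left.

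**Step 4: how often.** Count only stops on a stool-free period before the last interval while true output is still at least 1%.
- Lowest (2/2, p = 5%; two intervals at 1.41 and 1.00): 1 − 0.95² = 10%. The second interval sits exactly on the threshold.
- Highest (3/4 and 5/4, p = 10%; six intervals): 1 − 0.90⁶ = 47%.

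Fewer than half are stopped this way in every setting, and the median loss equals the daily-stool loss (0-1.3%).

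**Step 5: contrast with the first check.** With urine ignored, Days 6/7 are falsely passed only by two stool-free periods in a row: p² = 0.05² to 0.10² = 0.25-1%.

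**Sensitivity (total loss under the current rule).** With 20% of output in urine: 1.5-3.0% (slowest 2.6-4.8%). If the Day 7 period counts in the later check: 1.8-4.3% (slowest 3.7-6.8%).

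**The case against.** **The literal reading is one of two.** Excretion is measured from both matrices, so a site can fairly say that below 1% is not established without a homogenate. The protocol already holds inconclusive results at Days 6/7 and Day 15, and Protocol 9.5.3 sends faecal collection details to the SRM. This stands, and it makes the point a clarification rather than a design failure. It does not close the gap, because the later sentence lacks the inconclusive wording and is mandatory.

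**The later sentence says discharged, not that collection ends.** True. The end of collection follows from footnote 3 and from home collection being tied to Day 15. The inference is sound.

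**Stool-free days are made less likely.** Regular bowel habit is required, constipation is excluded, and hydration and prunes are allowed (Protocol 6.1, 6.2, 6.3.1). These reduce the chance, but an average of one a day does not guarantee a stool in every 24 h.

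**The consequences are limited.** Analysis of recovery is descriptive, no recovery threshold is set, and SAP Listings 40-41 and the individual plots would show where collection stopped. So the loss is visible, though not recoverable.

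Three stronger readings are tempting, and the documents do not support them:
- *The SAP lacks a missing-data rule for stool-free intervals.* None is needed. An empty interval correctly adds zero, and retained material is counted with the next collected stool.
- *The whole loss under the current rule comes from stool-free days.* Any 1% rule leaves a tail. Up to 1.3% is lost with daily stools.
- *The extension should also need two qualifying periods.* With daily stools, one period versus two differs by only 0-0.7 points under these assumptions, so that is a preference.

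**Conclusion.** The point holds as a minor-to-moderate weakness in the Period 2 collection-stopping wording. As written, a single stool-free period with low urinary radioactivity can end collection for a participant who is still excreting and truncate a primary endpoint for that participant.

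Under the stated assumptions, the mean loss attributable to stool-free periods is about 0.3-3.1 points of dose among extension participants. It is 2.8-5.1 in the slowest setting, which still excretes about 1.5% a day at 312-336 h, a case the protocol itself calls unlikely. About 10-47% of extension participants would be stopped on a stool-free period while true excretion is at least 1%. The typical (median) participant loses nothing extra.

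The effect across all six participants cannot be stated, because the number entering the extension is unknown. Nor do the documents show that recovery will be biased: that depends on site practice and on an SRM that was not supplied.

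**What to change.** Reconcile the Synopsis, Protocol 5.1 and 5.1.2, and SoA Period 2 footnotes 2, 3 and 12, and add one rule: a 24-h period without a faecal sample is inconclusive and cannot by itself satisfy the below-1% collection-stopping test, whether at Days 6/7, in the periods between, or at Day 15. If the SRM already says this, a cross-reference in those places is enough.

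In the same edit:
- State that a mixed Day 6/7 result (one period below 1%, one above) means collection continues. The conditions for leaving on Day 8 are not met in that case, but the bullet on staying does not clearly cover it either.
- State whether the Day 7 period counts in the later check.

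Cost: protocol wording, plus on average 0.3-1.8 more collection days for extension participants under the assumptions above, within the existing Day 15 limit. The remaining mean loss would be 0-1.2% of dose at a stool-free probability of 5-10%, the tail that a 1% rule leaves. No SAP change is needed.
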